7.3.2. Outcome definitions

PART I: Historical Cohort

The aim of the historical cohort is to understand treatment patterns for complicated influenza patients admitted to ICU and factors associated with treatment. Therefore, the outcome will be Neuraminidase Inhibitor treatment versus no Neuraminidase Inhibitor treatment.

PART II: Comparative Cohort

Clinical outcomes – primary endpoint:

- All-cause in-hospital mortality up to end of follow-up (defined in Section 7.7.1).

Clinical outcomes – secondary endpoints:

- All-cause in-hospital mortality up to end of follow-up
- All-cause in-hospital mortality at Day 7, 10 and 14 after hospital admission
- Ordinal scale for clinical course of influenza disease
 1. Discharged from hospital
 2. Not requiring supplemental oxygen
 3. Requiring supplemental oxygen
 4. In ICU, not on mechanical ventilation
 5. In ICU, on mechanical ventilation
 6. Death

Analyses will consider the ordinal scale at Day 7, 10 and 14 after treatment initiation/matching.

Clinical outcomes - exploratory

- All-cause in-hospital mortality up to end of follow-up
- Length of stay in hospital and in critical care unit/ICU
- Summary of associated complications of influenza (bacterial pneumonia, sepsis, myocarditis, encephalitis, acute respiratory distress syndrome, respiratory failure, bronchitis)

7.3.3. Confounders and effect modifiers

Outcomes will be summarised according to the following risk factors:

- Season/pandemic
- Country/centre
- Influenza strain/sub-type
- Age
- Sex
- Body mass index (BMI)
- Smoking status (Current, ex- smoker, never smoked)
- Vaccination status, other antiviral treatments, antibiotics
- Underlying co-morbidities including but not limited to:
 - Asthma
 - Chronic obstructive pulmonary disease (COPD)
 - Other pulmonary diseases
 - Other chronic conditions (e.g. Cardiovascular Disease, Chronic Kidney Disease, Diabetes, Neurological Disease and Obesity)
 - Immunocompromised
 - Pregnancy
 - Obesity
 - Prematurity
- Co-infecting viruses
- Duration of flu-specific symptoms prior to hospitalisation/treatment
- Presentation at admission (Influenza-like illness [ILI], pneumonia, otitis media [OM], sepsis etc.)
- Requiring supplemental oxygen
- Mechanical ventilation in ICU
- Days from hospital admission to ICU/critical care admission
- In-hospital corticosteroid administration (timing, drug, dose, frequency etc.)
- In-hospital antibiotic administration (timing, drug, dose, frequency etc.)
- Reason why patient has limited treatment options

7.4. Data sources

This study will only make use of hospital medical records.

7.5. Study size

The following assumptions are made with regard to the sample size estimation for the comparative cohort:

- There is no other difference between the IV zanamivir cohort and untreated cohort, except the treatment;
- The baseline mortality in the untreated group ranges between 5% and 25% representing differences in pathogenesis of potential circulating strains;
- The mortality odds ratio (treated vs. untreated) ranges between 0.20 and 0.80
- $\alpha=0.05$ and $\beta=0.20$
- A continuity correction was applied [Fleiss, 1980]

Based on the assumptions above, the sample sizes required to detect various odds ratios with 80% power at the 5% statistical level are described in [Table 1](#). For example, assuming mortality of 12% in unexposed patients and assuming a 1:1 treated vs untreated ratio, a minimum of 450 patients in each exposure arm would be required to demonstrate a statistically significant reduction in mortality with 80% power, assuming a true odds ratio of 0.5. Depending on the number of untreated patients in participating ICUs, the sample size estimation may need to be revisited after the feasibility study.

Table 1 Estimated sample size corresponding with varying treated/untreated ratio, mortality and odds ratios (OR)

Treated: Untreated	Mortality untreated	OR=0.20		OR=0.40		OR=0.50		OR=0.80	
		Treated	Not*	Treated	Not*	Treated	Not*	Treated	Not*
1:1	5%	343	343	686	686	1044	1044	7565	7565
	12%	142	142	292	292	450	450	3352	3352
	25%	68	68	148	148	233	233	1835	1835
2:1	5%	473	236	977	488	1502	751	11207	5595
	12%	198	99	419	209	651	325	4975	2484
	25%	96	48	214	107	341	170	2734	1365
3:1	5%	597	199	1263	421	1956	652	14823	4941
	12%	249	83	543	181	849	283	6585	2195
	25%	123	41	279	93	447	149	3624	1208

* Untreated

7.6. Data management

A separate Data Management Plan will be written before the start of this study outlining the procedures in more detail.

7.6.1. Data handling conventions

The eCRFs used to collect the data will include specific error checks to minimize data entry errors (formatting and range checks). Management of clinical data will be performed in accordance with applicable GSK standards and data cleaning procedures to ensure the integrity of the data, e.g., removing errors and inconsistencies in the data.

7.6.2. Resourcing needs

The implementation, management and closure of this study will be outsourced to a contract research organisation (CRO). The study will be overseen at GSK by a PhD level Epidemiologist.

Biostatistical and methodological issues will be addressed by a senior level statistician at GSK with expertise in observational data.

7.6.3. Timings of Assessment during follow-up

The final data collection time for both the historical and comparative cohorts of the study is at hospital discharge, the latest available date before study withdrawal or loss to follow-up, or at day 28 after hospital admission if a patient has not been discharged or has been re-admitted to hospital within the 28-day study period.

The dedicated research nurse(s) at each site will check medical charts of discharged patients to identify eligible patients. [Table 2](#) below outlines for which times each (group of) variable(s) of interest will be collected.

Table 2 Proposed exposure and outcome assessment intervals

Data variable	At hospital admission	Before ICU admission	At/after ICU admission	Hospital discharge OR Day 28 post-treatment
Demographics	X			
Influenza diagnostics/details (e.g. influenza strain/type, diagnostic test)	X			
Other risk factors (confounders/effect modifiers from Section 7.3.3)	X	X	X	
In-patient IV zanamivir treatment	X	X	X	X
Admission to critical care facilities (e.g. ICU/high dependency unit [HDU])	X		X	X
Ordinal scale clinical outcomes	X	X	X	X
Mortality in hospital		X	X	X

7.7. Data analysis

7.7.1. Essential analysis

All analyses will be performed in SAS 9.4. Descriptive analyses will be performed with continuous variables expressed as means with 95% confidence intervals or medians and ranges, as appropriate for the data distribution. Categorical variables will be expressed as frequency or proportion of patients in each category.

The sub-sections below are an outline of the types of analyses that are currently being considered. A detailed statistical analysis plan will be written before data collection for the comparative cohort starts.

PART I: Historical Cohort

A logistic regression analysis will be performed to identify factors associated with anti-influenza treatment versus no anti-influenza treatment. If sufficient data are available, the analysis will be repeated for IV zanamivir.

PART II: Comparative Cohort

Propensity scores will be derived from the predicted probability of IV zanamivir treatment estimated in a multivariable pooled logistic regression model with treatment/no treatment fitted as the binary outcome and the covariates listed in Section 7.3.3 above specified as explanatory variables. Treatment and exposure data will be captured separately for the pre- and post-ICU periods as per Section 7.6.3, and models will be stratified by season (to control for differences in severity) and by time since illness onset to facilitate appropriate matching. Standardised differences will be calculated to assess the balance achieved in the matched sample [Austin, 2011a]. If an insufficient number of matched pairs are obtained, alternative approaches e.g. propensity score stratification or inverse-probability of treatment weighting (IPTW) will be considered and the analysis modified accordingly [Cullen, 2009; Austin, 2011a]. Similarly, if only a small number of patients are exposed to IV zanamivir then a Disease Risk Score-match approach will be applied [Glynn, 2012]. For analysis of within-hospital mortality fitted as the binary outcome, the same method will be applied.

If there are sufficient data, propensity score-matched samples will be created to compare: early (≤ 2 days from symptom onset to treatment initiation) versus late IV zanamivir treatment (> 2 days from symptom onset to treatment initiation); early IV zanamivir treatment versus no treatment; late IV zanamivir treatment versus no treatment. Analyses will also be conducted in the subset of mechanically-ventilated patients, and, if sufficient data are available, an analysis will be conducted on patients infected with influenza viruses where resistance is confirmed. If numbers are sufficient, further stratified analyses will be performed for adults and children (aged < 16 years) as well as for immunocompromised patients.

Following matching, patients will accrue time-at-risk from ICU admission (for IV zanamivir patients who initiated prior to ICU admission), treatment initiation (for IV zanamivir patients who initiated in the ICU) or ICU admission (comparator patients); as the study is conducted among ICU-admitted patients, person-time prior to ICU admission is immortal. Patients will be followed up until they experience the event of interest (death) or they are censored (the earlier of hospital discharge or 28 days post treatment/matching [as applicable]). For the secondary objectives described below censoring will be modified as appropriate (7, 10 or 14 days post treatment/matching).

Primary objective: all-cause in-hospital mortality to end of follow-up

A matched Cox regression analysis will be performed to estimate the association between IV zanamivir treatment and mortality during hospital stay. The treated vs. untreated groups will be compared to obtain the hazard ratio for in-hospital survival. Kaplan-Meier plots will be produced for graphical comparison of survival in the two groups.

Secondary objective: crude all-cause in-hospital mortality to end of follow-up

A crude estimate of the hazard ratio, based on the unmatched sample, will also be obtained using a time-dependent Cox regression model stratified by season, to control for differences in severity.

Secondary objective: All-cause in-hospital mortality at Day 7, 10 and 14

A regression analysis, similar to the primary analysis, will be performed on available mortality data at Day 7, 10 and 14 post treatment/matching.

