7.7.2. Exploratory analysis

Inverse Probability of Censoring Weighted (IPCW) Analysis

The proposed matching strategy seeks to minimise bias by not utilising future information to define exposure status [Hernan, 2016]. Accordingly, patients who are matched as controls may go on to receive IV zanamivir and treated patients may discontinue IV zanamivir. To examine the effect of this potential exposure misclassification, if observed to some ($\geq 10\%$) degree, (IPCW) analysis will be performed for the primary objective analysis. Patients who do not persist to their exposure status will be censored at the time of non-persistence, and stabilised weights – generated from a pooled logistic regression model with non-persistence fitted as the outcome variable and the parameters described in Section 7.3.3 included as explanatory variables – will be utilised in a weighted pooled logistic regression analysis of the effect of IV zanamivir treatment on all-cause within-hospital mortality.

Ordinal Scale at Day 7, 10 and 14

A proportional odds regression model will be fitted to estimate the odds of different categories of the ordinal scale at Day 7, 10 and 14, and their 95% confidence intervals, in the IV zanamivir group compared with the untreated group. Results will be presented for two levels of adjustment: (i) unadjusted (i.e., crude comparison) and (ii) using propensity score stratification with additional adjustment for ICU ventilation on Day 1, inpatient antibiotics and systemic corticosteroids. Patients will be assigned to the point on the ordinal scale based on the information for that day and not for the period up to and including that day (e.g. 0-7, 0-10, 0-14 days).

Length of hospital/ICU admission

Matched t-tests, or alternative non-parametric tests, will be performed to compare length of hospital stay and length of ICU admission between IV zanamivir and no IV zanamivir treatment patients (and, if sufficient data exist, by early/late treatment).

Associated complications

Descriptive analyses of the proportion of each treatment group with associated complications of influenza (bacterial pneumonia, myocarditis, encephalitis, sepsis, acute respiratory distress syndrome, respiratory failure, bronchitis) during ICU stay will also be reported.

For optimal comparability, the primary and secondary analyses will be repeated using the following definitions, which are similar to what was used in the Phase 3 clinical trial:

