7.9. Limitations of the research methods

Medical records may not always be complete, potentially leading to incomplete data for specific patients (historical and not captured in the clinical history). The historical cohort will inform on completeness of data and may promote increased data capture for the main comparative study. To further minimise missing data, identified hospitals will be asked if they can provide a minimum dataset from their medical records. Training will also be provided to ensure that all participating health care providers understand the importance of complete medical records. The minimum dataset requirements will also help prevent any major differences between countries, with regard to which variables are recorded.

Although measures are in place to ensure the collected hospital records are fairly complete, they are not linked to other databases capturing patient health post-discharge. Therefore, this study design does not include any collection of mortality data after

hospital discharge. It is possible that Day 28 survival data will not be available for some patients, unless the patient is readmitted to the same hospital.

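### Live discharge is censored instead of handled as a competing event, so the Kaplan-Meier curves overstate in-hospital mortality and the Cox hazard ratio does not contrast the proportions dying

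*Protocol*

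**What the plan says.** Protocol 7.3.2 sets the primary endpoint as "All-cause in-hospital mortality up to end of follow-up (defined in Section 7.7.1"). Section 7.7.1 then fixes three things:

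- **Censoring.** Patients without the event are followed until "they are censored (the earlier of hospital discharge or 28 days post treatment/matching [as applicable"].
- **Model.** "A matched Cox regression analysis will be performed to estimate the association between IV zanamivir treatment and mortality during hospital stay". The result is a hazard ratio; the abstract says the same.
- **Display.** "Kaplan-Meier plots will be produced for graphical comparison of survival in the two groups".

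The mortality comparisons at Days 7, 10 and 14 use a similar regression with a shorter horizon: "For the secondary objectives described below censoring will be modified as appropriate (7, 10 or 14 days post treatment/matching").

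Section 7.9 says that "this study design does not include any collection of mortality data after" discharge. Section 7.5 sizes the study on proportions dying: 12% in untreated patients, odds ratio 0.5, 450 per arm.

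**The concern.** Censoring at discharge has different consequences for the two outputs.

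One minus Kaplan-Meier can be read as the probability of in-hospital death only if discharged patients would have gone on dying in hospital at the rate of those who stayed. Those who stay are the sicker patients, and those who have left alive cannot have the event in that stay. The curve therefore overstates mortality.

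The Cox model needs no such assumption to estimate the hazard of death among patients still in hospital. However, the proportion dying depends on that hazard and on how long patients stay exposed to it. If treatment alters the speed of discharge, the hazard ratio and the contrast of proportions can differ in size and even in direction.

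The protocol itself allows for an effect on discharge. It compares length of hospital and ICU stay between groups (7.7.2), and it makes discharge the best category of the ordinal scale (7.3.2). What is at stake is the headline result of a post-authorisation study meant to demonstrate clinical effectiveness (5.1).

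**Working it through.** **The plan's own figure.** Odds of death in the untreated are 0.12/0.88 = 0.1364. Halved they are 0.0682, so treated mortality is 0.0682/1.0682 = 6.38%. The two-sided 5%, 80%-power formula for two proportions with continuity correction gives 449 per arm against the stated 450. The size is thus built on proportions dying. Expected deaths are 450 × 0.12 + 450 × 0.0638 = 54 + 28.7 = 82.7.

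**Model for the check.** Assume constant daily hazards d (death) and s (live discharge):

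- True in-hospital mortality by day 28: d/(d+s) × (1 − exp(−28(d+s))).
- One minus Kaplan-Meier with discharge censored: 1 − exp(−28d).
- Planned Cox hazard ratio: d(treated)/d(untreated).

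The protocol gives no discharge rates. I take s = 0.04, 0.06 and 0.08 per day and solve for the d that gives a true 12%.

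**Kaplan-Meier**

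| s per day | d per day | Median stay (days) | Still in hospital at day 28 | True mortality | 1 − KM at day 28 |
|---|---|---|---|---|---|
| 0.04 | 0.00777 | 14.5 | 26% | 12% | 19.6% |
| 0.06 | 0.00975 | 9.9 | 14% | 12% | 23.9% |
| 0.08 | 0.01194 | 7.5 | 8% | 12% | 28.4% |

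For s = 0.04, 28d = 0.2176 and 1 − exp(−0.2176) = 19.6%. Over a wider assumption, from 50% down to 5% still in hospital at day 28, the Kaplan-Meier figure runs from 15.3% to 31.5%. At day 14, with s from 0.04 to 0.08, the true figure is 7.9% to 9.4% and Kaplan-Meier shows 10.3% to 15.4%.

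**Cox hazard ratio** (untreated arm as above; s in the treated arm multiplied by the factor shown; ranges run from s = 0.04 to 0.08)

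| Scenario | Discharge on drug | Planned hazard ratio | What happens to mortality |
|---|---|---|---|
| Odds ratio 0.5 | × 1 | 0.510 to 0.505 | 12% vs 6.38% |
| Equal mortality | × 1.1 | 1.05 to 1.08 | 12% in both |
| Equal mortality | × 1.25 | 1.12 to 1.20 | 12% in both |
| Equal mortality | × 1.5 | 1.255 to 1.405 | 12% in both |
| Equal mortality | × 0.75 | 0.88 to 0.82 | 12% in both |
| Death hazard unchanged | × 1.5 | 1.0 | 12% falls to 9.75% to 8.8% (odds ratio 0.79 to 0.71) |
| Odds ratio 0.5 | × 1.5 | 0.64 to 0.71 | 12% vs 6.38% |

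A simulation of 50,000 per arm, with 10% of untreated patients still in hospital at day 28, agrees. With the death hazard unchanged and discharge 1.5 times faster, Cox with discharge censored gave 0.97. With discharged survivors held event-free to day 28 it gave 0.72, and simulated mortality was 12.4% against 9.0%.

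**Search for a repair elsewhere.** The inverse-probability-of-censoring analysis in 7.7.2 concerns exposure status only: "Patients who do not persist to their exposure status will be censored at the time of non-persistence". Section 7.7.1 has one sentence on a binary outcome, "For analysis of within-hospital mortality fitted as the binary outcome, the same method will be applied", but it closes the propensity-score paragraph and is not tied to the primary objective. Section 7.9 admits that day-28 survival may be unknown after discharge, but does not connect this with the censoring rule.

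**The case against.** Most of the case on the other side concerns the Cox model, and much of it stands.

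- **The Cox analysis is not invalid.** A reader might infer that it is, or that discharged patients are counted as still at risk. Neither is right. A censored patient leaves the risk set, and the cause-specific ratio is a recognised measure of the association that 7.7.1 asks for. The fair criticism is narrower: it does not compare the proportions dying.
- **Divergence needs an effect on discharge.** With equal discharge rates the hazard ratio is about 0.51 where the odds ratio is 0.5, and with 1.1-fold faster discharge and equal deaths it is only 1.05 to 1.08. The documents give no expected effect on discharge.
- **Faster discharge does not by itself push the ratio against the drug.** Equal mortality with 1.5-fold faster discharge implies a daily death hazard 26% to 41% higher on drug, and the model reports that correctly. If the drug only speeds discharge, the ratio stays at 1.0 and misses a fall in mortality.
- **The sample size is not wrong.** The 450 per arm reproduces, and the fix leaves it unchanged.
- **The protocol is partly an outline.** 7.7.1 says that a detailed analysis plan will follow. The ordinal scale keeps discharged patients in view, length of stay is compared, and Kaplan-Meier is intended only as a graph. Even so, the censoring rule, model and plot are stated outright, and an analysis plan that follows them inherits the problem.
- **Discharge is not always final.** Sections 7.6.3 and 7.9 mention readmission, so any remedy must say how a death on readmission counts.

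**Conclusion.** The point holds in two parts of different strength. The Kaplan-Meier curves overstate in-hospital mortality whenever patients leave alive before day 28; only the size is assumed (a true 12% shown as about 20% to 28% at 0.04 to 0.08 discharges per day). The Cox hazard ratio is a legitimate cause-specific estimate, but it is not the contrast of in-hospital mortality that the primary objective names and that 7.5 is sized on. Its departure from that contrast is conditional: negligible when discharge is equally fast in both arms, about 1.25 to 1.40 against no difference in deaths when discharge on drug is 1.5 times faster, and 1.0 against a fall to about 9% to 10% when only discharge changes. All sizes rest on constant hazards and on discharge rates and ratios that the protocol does not give. The documents do not support the stronger conclusion that the planned Cox result will be misleading in this study, because nothing in them shows how treatment affects discharge. They show only that the plan has no protection if it does.

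**What to change.** 1. Replace the Kaplan-Meier plots with cumulative incidence curves of in-hospital death, with live discharge as the competing event.
2. Make the primary contrast in-hospital death by day 28 from index, with patients discharged alive held event-free to that day. Matched binary regression gives the odds ratio of 7.5 directly; a Fine-Gray model is the alternative.
3. Report the discharge-censored Cox hazard ratio beside it, labelled as cause-specific.
4. Do the same at Days 7, 10 and 14.
5. State how deaths on readmission within 28 days count, given 7.6.3 and 7.9, and how a transfer to another hospital is classed.

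The cost is analysis-plan wording and programming; discharge and in-hospital death are already collected and 450 per arm is unaffected. One check is needed. The text of 7.6.3 ends collection at day 28 after hospital admission for patients not yet discharged, whereas its Table 2 and 7.7.1 count from treatment or matching. A fixed day-28 endpoint needs one origin, with inpatients followed to it.

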7.7.2. Exploratory analysis

Inverse Probability of Censoring Weighted (IPCW) Analysis

The proposed matching strategy seeks to minimise bias by not utilising future information to define exposure status [Hernan, 2016]. Accordingly, patients who are matched as controls may go on to receive IV zanamivir and treated patients may discontinue IV zanamivir. To examine the effect of this potential exposure misclassification, if observed to some ($\geq 10\%$) degree, (IPCW) analysis will be performed for the primary objective analysis. Patients who do not persist to their exposure status will be censored at the time of non-persistence, and stabilised weights – generated from a pooled logistic regression model with non-persistence fitted as the outcome variable and the parameters described in Section 7.3.3 included as explanatory variables – will be utilised in a weighted pooled logistic regression analysis of the effect of IV zanamivir treatment on all-cause within-hospital mortality.

Ordinal Scale at Day 7, 10 and 14

A proportional odds regression model will be fitted to estimate the odds of different categories of the ordinal scale at Day 7, 10 and 14, and their 95% confidence intervals, in the IV zanamivir group compared with the untreated group. Results will be presented for two levels of adjustment: (i) unadjusted (i.e., crude comparison) and (ii) using propensity score stratification with additional adjustment for ICU ventilation on Day 1, inpatient antibiotics and systemic corticosteroids. Patients will be assigned to the point on the ordinal scale based on the information for that day and not for the period up to and including that day (e.g. 0-7, 0-10, 0-14 days).

Length of hospital/ICU admission

Matched t-tests, or alternative non-parametric tests, will be performed to compare length of hospital stay and length of ICU admission between IV zanamivir and no IV zanamivir treatment patients (and, if sufficient data exist, by early/late treatment).

Associated complications

Descriptive analyses of the proportion of each treatment group with associated complications of influenza (bacterial pneumonia, myocarditis, encephalitis, sepsis, acute respiratory distress syndrome, respiratory failure, bronchitis) during ICU stay will also be reported.

For optimal comparability, the primary and secondary analyses will be repeated using the following definitions, which are similar to what was used in the Phase 3 clinical trial:

- Early treatment: ≤ 4 days after symptom onset to treatment initiation;
- Late treatment: >4 days after symptom onset to treatment initiation.

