7.3.1. Exposure definitions

PART I: Historical Cohort

The aim of the historical cohort is to understand treatment patterns for ICU-admitted influenza patients and factors associated with treatment. Therefore, included patients will be those hospitalised with influenza and admitted to ICU.

PART II: Comparative Cohort

All subjects in the IV zanamivir treatment cohort are exposed to at least 1 dose of IV zanamivir. Subjects in the untreated comparator arm are not treated with IV zanamivir at the time of matching. In this approach, which is analogous to the intention-to-treat analyses employed in clinical trials, matched patients will retain their exposure status during the analysis regardless of future treatment status (IV zanamivir discontinuation/initiation in cases/matched comparators respectively). The effect of this potential exposure misclassification will be investigated (exploratory analysis; Section 7.7.2).

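### The exploratory IPCW analysis names one non-persistence model with no exposure-arm term, although non-persistence means stopping the drug in one arm and starting it in the other, so its weights may leave most of the selection bias in place

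*Protocol*

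**What the plan says.** Matched patients keep their exposure status in the primary analysis whatever happens later. Section 7.3.1 spells out what later change means: "IV zanamivir discontinuation/initiation in cases/matched comparators respectively". Section 7.7.2 repeats it: "patients who are matched as controls may go on to receive IV zanamivir and treated patients may discontinue IV zanamivir".

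If at least 10% of patients change, an IPCW analysis of the primary objective follows: "Patients who do not persist to their exposure status will be censored at the time of non-persistence, and stabilised weights" are applied. These weights are "generated from a pooled logistic regression model with non-persistence fitted as the outcome variable and the parameters described in Section 7.3.3" as explanatory variables, and they "will be utilised in a weighted pooled logistic regression analysis of the effect of IV zanamivir treatment on all-cause within-hospital mortality".

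Section 7.3.3 lists season, centre, strain, demographics, co-morbidities, ventilation, corticosteroids and similar factors. Its nearest entry to exposure is "Vaccination status, other antiviral treatments, antibiotics". IV zanamivir arm is not on the list. The protocol does not say whether the weight model is fitted by arm, and it does not describe the numerator of the stabilised weights.

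**The concern.** Censoring at the time of switching is informative if switching depends on prognosis. The weights remove that selection only if they reflect each patient's own probability of being censored, given covariates and arm. Here one outcome variable covers two different clinical decisions, and the named predictors cannot tell them apart.

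Section 7.9 itself expects sicker patients to be channelled to the drug, so severity plausibly drives initiation among comparators. Nothing suggests that the same coefficient, or the same rate, governs stopping among treated patients.

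At stake is the analysis that 7.3.1 points to for exposure misclassification in the primary comparison. If its weights do little, a reader could take leftover selection for information about the drug. The point is separate from which stops count as discontinuation and from how often covariates are updated. It remains if both are settled.

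**Working it through.** **The plan's own figures.** The protocol gives no figure for this analysis. Its sample size is needed below only for scale. With 12% untreated mortality and OR 0.5, treated odds are 0.5 × 0.12/0.88 = 0.0682, so treated mortality is 0.0682/1.0682 = 6.38%. Two-sided 5%, 80% power and 1:1 give 415 per arm uncorrected and 449 with the Fleiss continuity correction, against 450 stated in 7.5. It reproduces.

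**Why weights without arm do not help.** Let n_a(v) be the uncensored patients in arm a at covariate level v, and w(v) a weight that ignores arm. The between-arm odds ratio for v after weighting is [n₁(1)w(1)/n₁(0)w(0)] ÷ [n₀(1)w(1)/n₀(0)w(0)]. The weights cancel. Any imbalance that censoring has created between the arms stays as it was.

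**Daily model (all inputs assumed).**
- Half of each arm is ventilated.
- Daily death probability is 0.0015 if not ventilated and 0.0080 if ventilated. Untreated 28-day mortality is 1 − ½(0.9985²⁸ + 0.9920²⁸) = 1 − ½(0.9588 + 0.7986) = 12.1%, close to the protocol's 12%.
- Comparators start at 0.5% per day (not ventilated) or 2% (ventilated). Treated patients stop at 2% or 0.5%. Non-persistence is about 26-27% per arm.

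With both arms combined, the daily switching probability at the start is (0.5% + 2%)/2 = 1.25% at either ventilation level. The stabilised weight is 0.9875/0.9875 = 1: no weighting.

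The leftover selection at day 14, ignoring deaths:
- Comparators still uncensored: ventilated 0.98¹⁴ = 0.754, others 0.995¹⁴ = 0.932. Ventilated share 0.754/1.686 = 0.447. In the treated arm it is 0.553.
- Mean daily hazard, inert drug: comparators 0.447 × 0.0080 + 0.553 × 0.0015 = 0.00441; treated 0.553 × 0.0080 + 0.447 × 0.0015 = 0.00510. Ratio 1.16.

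The full 28-day weighted pooled logistic calculation with day effects gives:
- Inert drug: 1.15 unweighted, 1.15 with one model, 1.15 with an arm main effect, 1.00 with arm-specific models. If deaths are counted before switching within a day, 1.15 becomes 1.14.
- True daily HR 0.52: 0.61, 0.61, 0.61 and 0.53.
- Switching rates halved or doubled, inert drug, one model: 1.08 or 1.31.
- Severity drives comparator initiation only, with treated patients stopping at a flat 1% per day: 1.08 with one model, 1.00 arm-specific.

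**Simulation (assumed inputs).** It used 28 daily intervals, a time-varying severity score that raises the death hazard, comparator mortality about 10%, and 40,000 patients × 6 replicates. The true odds ratio under full persistence is 0.51.

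| Severity effect on switching (non-persistence, treated/comparator) | Unweighted | One model, no arm | Arm main effect | Arm-specific |
|---|---|---|---|---|
| Opposite directions (47%/46%) | 0.67 | 0.67 | 0.67 | 0.52 |
| Opposite, unequal rates (70%/33%) | 0.69 | 0.69 | 0.66 | 0.51 |
| Comparators only (38%/46%) | 0.61 | 0.62 | 0.61 | 0.52 |
| Opposite, near the trigger (10%/9%) | 0.54 | 0.54 | 0.54 | 0.51 |
| Same direction, same rate (47%/46%) | 0.51 | 0.51 | 0.51 | 0.51 |
| Same direction, unequal rates (70%/33%) | 0.42 | 0.40 | 0.55 | 0.56 |

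In the last row the two right-hand values are imprecise (standard error about 0.09 on the log scale).

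**The case against.** The strongest reply is that the text is an outline. It does not say that only the 7.3.3 factors enter, nor that the arms are combined. The word pooled normally means pooled over person-time. Section 7.3.3 lists confounders, with exposure defined elsewhere, and it also omits the follow-up-day term that any such model needs. A detailed SAP is promised, and 7.7.1 introduces its own analyses with "The sub-sections below are an outline of the types of analyses that are currently being considered". Much of this stands: a reader might infer that the protocol rules out arm terms, and it does not. But 7.7.2 does name the model form, a single outcome and a predictor list, and an SAP that follows it as written inherits the fault. This is more than detail left open.

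A reader might also infer that the weights cannot correct the bias, that the check is biased against the drug, or that it could refute a real effect. The documents support none of these. With an identical process in both arms one model does no harm. The direction can reverse: the last row of the table favours the drug. The 1.15 case uses mirror-image rates, for which the combined severity effect cancels by construction, and with a real effect it still shows benefit (0.61).

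The shift is also modest against sampling error. At 450 per arm, expected deaths are 450 × 0.12 = 54 and 450 × 0.0638 ≈ 29, so the standard error of the log hazard ratio is about √(1/54 + 1/29) = 0.23 before any censoring. The shift ln(0.61/0.53) = 0.14 is about 0.6 of that.

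**Conclusion.** The concern holds in a limited form. As written, the IPCW weights come from one non-persistence model whose named predictors omit exposure arm, although the event differs by arm. Unless switching follows the same process in both arms, such weights may leave most of the selection bias from artificial censoring. Under the assumed rates an inert drug shows a hazard ratio of about 1.08 to 1.15 instead of 1.00. Near 10% non-persistence the bias is small (0.54 against 0.51 in the simulation). The documents give neither switching rates nor their determinants, so size and direction are illustrative. The analysis is exploratory and runs only if at least 10% non-persistence is observed. The primary matched Cox analysis keeps exposure status as matched and is not affected. The change is worth making because it is nearly free.

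**What to change.** State in 7.7.2, and carry into the SAP, that the numerator and denominator non-persistence models are fitted separately in the IV zanamivir and comparator arms. A single model that includes arm with arm-by-covariate and arm-by-time interactions would also serve. An arm main effect alone is not enough when covariate effects differ by arm, as the first row of the table shows.

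The cost is one sentence and one more model fit, with no new data. Weights will be somewhat less stable if non-persistence events in one arm are few.
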